The 3-day surveillance period has been defined based on the predicted half-life of the drug (i.e. sufficient time to determine the terminal half-life and maintain the clinical and biological surveillance up to final drug elimination). Following review of interim results of the 3 first cohorts (10 mg, 20 mg and 40 mg), GM half-life of DNDI-6148 was around 20 hours and five half-lives corresponds to 100 hours. All the volunteers will remain under medical surveillance for 72 hours (presence of a medical doctor in the facility 24h/24 during the hospitalisation of volunteers), and for the cohorts 160 mg, 260 mg, 380 mg and 500 mg, the collection of blood PK samples has been extended up to 120 hours

The study will proceed to the next dose level only if the safety results are acceptable, as agreed by the Safety Review Committee (gathering at least the Sponsor medical responsible, a pharmacokineticist and the Investigator) and if stopping rules are not met. A minimum of 6 subjects per cohort with complete safety data available will be required for decision to proceed to the next dose level (i.e. minimum of 4 subjects under active). All safety data available at the time of the Safety Review Committee meeting will be taken into account for decision on dose-escalation (including safety data from previous cohorts).

At the end of the Safety Review Committee meeting, the following decisions can be taken:

- Dose escalation will continue as scheduled;
- An intermediate dose between the current dose and the following dose will be administered to the next cohort;
- A lower intermediate dose, between the current dose and the dose administered in the previous cohort will be administered to the next cohort;
- The current dose will be repeated in the next cohort;
- The study will be stopped.

According to the conclusion of this meeting, the formal agreement/disagreement will be signed by both the Sponsor and the Investigator.

One cohort can be duplicated to enlarge the number of subjects in one sub-group in case of need. In case the stopping rules are met, no duplication of the same cohort will be possible.

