6. ASSESSMENT OF PHARMACOKINETIC EVALUATION

6.1. Specification of the pharmacokinetic parameters

6.1.1. Plasma

The following pharmacokinetic parameters will be determined from DNDI-6148 concentrations:

- Main DNDI-6148 PK parameters:
 - o AUC_{0-∞} (h*ng/mL): area under the plasma concentration-time curve from administration up to infinity with extrapolation of the terminal phase;
 - o C_{max} (ng/mL): observed maximum plasma concentration,
- Other DNDI-6148 PK parameters:
 - o AUC₀₋₂₄: AUC from administration up to 24h
 - AUC_{0-t:} area under the plasma concentration-time curve from administration up to the last quantifiable concentration at time t
 - AUC_{0-t}/D: AUC_{0-t} divided by dose
 - o AUC_{0-∞}/D, : AUC_{0-∞} divided by dose
 - o C_{max}/D,: C_{max} divided by dose
 - o tmax_(h): first time to reach Cmax
 - o t_{1/2} (h): plasma elimination half-life
 - o MRT (h): Mean time of drug presence in plasma
 - o CL/F (mL/h): Apparent total clearance of the drug from plasma after oral administration
 - o Vz/F (L): Apparent volume of distribution
 - o ke: terminal elimination rate constant
 - o %AUCextra: % of AUC extrapolated

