6.1.2. Urine

The amount and concentration of DNDI-6148 will be measured. The appropriate specific PK parameters to be calculated will be decided according to concentration.

The following parameters will be calculated from urine data for DNDI-6148:

- **Ae(0-t)** Total amount excreted over 24 h and 72 h (*i.e.* t = 24 or 72).
- **Fe** The fraction of the dose excreted in urine over 24 h and 72 h.
- CLr The renal clearance of DNDI-6148.

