6.3. Analytical methods

A validated internally standardized liquid chromatography tandem mass spectrometry (LC/MS-MS) method will be used for the analysis of DNDI-6148 in acidified K₂EDTA human plasma and acidified human urine.

The Lower limit of quantification (LLOQ) of DNDI-6148 in plasma is 1 ng/ml in plasma and 10 ng/ml in urine.

Bioanalysis will be carried out at SGS Life Sciences, Wavre, Belgium. The bioanalytical procedures of the laboratory are certified according to Good Laboratory Practice (GLP).

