8.2.2. Description by type of visit

D-1

- Subject admission;
- Diagnostic test of SARS-CoV-2;
- Alcohol breath test;
- Urine drug screen;
- Physical examination
- Complete neurological examination;
- AE/Concomitant medication check;
- Laboratory safety (hematology, biochemistry, hemostasis, hormonology and urinalysis) will be performed in order to have the results before the Day 1 morning drug administration);
- Blood pressure, heart rate and body temperature;
- ECG
- C-SSRS evaluation Bond & Lader questionnaire.

D1

- Before administration
 - Physical examination;
 - ECG in triplicate before the T0 dosing time
 - Blood pressure, heart rate and body temperature at T0h;
 - AE/Concomitant medication check;
 - Blood sampling (Pre-dose);
 - Predose urine sample;
 - Start of Holter recording 70 minutes before dosing;
 - Randomization.
- oral administration in fasting condition.
 - AE/Concomitant medication check (any time)
 - Complete neurological examination around T6h;
 - Blood pressure, heart rate and body temperature at T1h, T1h30 (only for the cohorts 10 mg, 20 mg, 40 mg and 80 mg), T2h, T2h30, T3h, T4h, T5h (only for the cohorts 160 mg, 260 mg, 380 mg and 500 mg), T6h, T12;
 - ECG in single at T1h, T2h, T3h, T4h, T6h, T9h, T12h;
 - C-SSRS evaluation Bond & Lader questionnaire around T6h;
 - Holter 24h-hours recording;
 - Blood sampling (T30min, T1h, T1h30min (only for the cohorts 10 mg, 20 mg, 40 mg and 80 mg),
 T2h, T2h30min, T3h, T4h, T5h (only for the cohorts 160 mg, 260 mg, 380 mg and 500 mg), T6h,
 T9h, T12h);
 - Urine collection:]T0-T12h],]T12h-T24h].

D2

- Physical examination;
- Laboratory safety (hematology, biochemistry, hemostasis and urinalysis);
- Blood pressure, heart rate and body temperature
- End of 24h Holter recording (after blood sampling T24h);
- AE/Concomitant medication check (any time);
- Blood sampling (T24h);
- ECG in single;
- Urine collection]T24h-T48h].

D3

- Blood pressure and heart rate and body temperature;
- ECG in single;
- Blood sampling (T48h);
- AE/Concomitant medication check.
- Urine collection]T48h- T72h].

D4: (end of study visit for the cohorts 10 mg, 20 mg, 40 mg and 80 mg))

- Physical examination (including weight);
- Complete neurological examination,
- Laboratory safety (hematology, biochemistry, hemostasis, hormonology and urinalysis);
- Blood pressure, heart rate and body temperature;
- ECG in single;
- C-SSRS evaluation Bond & Lader questionnaire;
- Blood sampling (T72h);

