In case, $AUC_{0-\infty}$ could not be considered as reliable in a majority of subjects (e.g. too large percentage of extrapolation, poor quality of k_e determination), dose proportionality assessment will be performed on AUC_{0-t} values.

The estimate obtained for β is a measure of dose proportionality. The estimate of β together with its 90% CI (β_{l} , β_{u}) will be presented to quantify the degree of non-proportionality.

The dose proportionality will be confirmed if the 90% CI of β (β_I , β_u) is contained completely within the following critical region:

$$\left[\Theta_{L};\Theta_{H}\right] = \left[1 + \frac{\log(0.8)}{\log(r)};1 + \frac{\log(1.25)}{\log(r)}\right]$$

where r, defined as the dose ratio, is equal to h/I, h being the highest dose and I the lowest dose.

In this decision rule, the dose proportionality will be analyzed as an equivalence problem. If the 90% CI is excluded completely from the critical region $\left[\Theta_L;\Theta_H\right]$ defined here above, the hypothesis of dose proportionality is rejected. If the 90% CI of β includes the lower or the upper bound of the critical region, no conclusion can be done on dose proportionality. The proportionality will be tested at a 5% significance level.

The calculation of the increase in AUC and C_{max} for a two-fold increase in dose will be performed by substituting the value of β in the equation 2^{β} . CI for this ratio will be obtained by substituting β_{l} and β_{u} in the equation 2^{β} .

Assessment of the dose proportionality will be performed on the complete dose range. In case of departures from linearity or of negative conclusion of dose proportionality on the complete dose range, further investigation using the same methodology might be done on a restrained dose range.

The statistical package SAS[®] v.9.4 will be used to perform all statistical analyses.

Pharmacodynamic

In case the Holter data are analysed, the following analyses will be reported in a separate report:

All ECG parameters for PD analysis will be extracted in triplicate from 24-hours Holter recording. Extraction will be matched to PK sampling time and triplicate values will be averaged in order to obtain one single value per time point. Individual data listings and descriptive statistics by dose level and time point will be performed.

All parameters will be presented descriptively and graphically on raw data and changes from baseline by dose level and time points.

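### The AUC0-t fallback for dose proportionality compares 72-hour areas at 10-80 mg with 120-hour areas at 160-500 mg, so beta is biased upward whenever it is used

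*Protocol*

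**What the plan says.** Section 11.1.3 fits a power model to AUC and Cmax over all dose levels. It confirms proportionality if the 90% CI of beta lies inside 1 + log(0.8)/log(r) to 1 + log(1.25)/log(r), where r is the ratio of highest to lowest dose. If AUC0-∞ "could not be considered as reliable in a majority of subjects", with a large extrapolated share or a poorly determined ke given as examples, then "dose proportionality assessment will be performed on" AUC0-t. No common cut-off time is set for that case.

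Section 6.1.1 defines AUC0-t as the "area under the plasma concentration-time curve from administration up to the last quantifiable concentration at time t".

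The sampling horizon differs by cohort. In section 8.2.2, Day 4 (the 72 h sample) is the "end of study visit for the cohorts 10 mg, 20 mg, 40 mg and 80 mg". For 160, 260, 380 and 500 mg, section 3.3.3.2 says "the collection of blood PK samples has been extended up to 120 hours". The reason given is that, in the first three cohorts, "GM half-life of DNDI-6148 was around 20 hours and five half-lives corresponds to 100 hours". Table 8 shows the same split.

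**The concern.** A fallback based on AUC0-t is fair only if every dose group is followed over the same span, or if concentrations become unquantifiable before sampling stops. Here the span changes once, between 80 and 160 mg, and always in favour of the higher doses. A drug with exactly proportional exposure would then give a beta above 1.

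The acceptance region is narrow because r = 50, so a modest step uses up much of it. If the fallback is invoked because extrapolation is large, half-lives are long, and that is where the artefact is largest. AUC0-t and AUC0-t/D are also named in the secondary objectives and summarised by dose level whether or not the fallback is used, so the unequal span reaches those tables too.

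**Working it through.** **The plan's own figure.** 5 × 20 h = 100 h, as section 3.3.3.2 states. This is the reason for sampling beyond 72 h in the upper cohorts.

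**Does the quantification limit equalise the spans?** The lower limit "of DNDI-6148 in plasma is 1 ng/ml in plasma" (section 6.3). Predicted Cmax is 509 ng/mL at 10 mg and 18105 ng/mL at 500 mg (Table 5). At a 20 h half-life:
- 10 mg at 72 h: 509 × 2^(−72/20) = 42 ng/mL. With a Cmax ten times lower it would still be 4.2 ng/mL.
- 500 mg at 120 h: 18105 × 2^(−120/20) = 283 ng/mL.

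Both exceed 1 ng/mL, so the schedule sets t: 72 h in one group of cohorts and 120 h in the other.

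**Bias in beta.** Under mono-exponential decline with half-life h, the share of the total area captured by time T is f(T) = 1 − 2^(−T/h). The step on the log scale is s = ln[f(120)/f(72)]. With six active subjects per dose, the bias is the least-squares slope of that step on ln(dose). Over the eight doses, Sxx = 14.23 and the cross-product of ln(dose) with the indicator for 160 mg and above is 4.711, so bias = (4.711/14.23) × s = 0.331 × s. The margin is ln(1.25)/ln(50) = 0.057, giving a region of 0.943 to 1.057.

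| Half-life (h) | f(72) | f(120) | Ratio | Bias | Share of margin |
|---|---|---|---|---|---|
| 11 (predicted) | 98.9% | 99.95% | 1.010 | +0.003 | 6% |
| 20 (observed) | 91.8% | 98.4% | 1.073 | +0.023 | 41% |
| 30 | 81.1% | 93.8% | 1.157 | +0.048 | 84% |
| 31 | 80.0% | 93.2% | 1.164 | +0.050 | 88% |
| 40 | 71.3% | 87.5% | 1.228 | +0.068 | 119% |

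Bias equals the margin at about 34 h. With a common span, s = 0 and the bias is zero.

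**Departure from one exponential.** Section 1.2.1.2 allows for an initial phase of about 4 h. If 25%, 50% or 75% of the area lay in it (assumed), with a 20 h terminal phase, the bias would be +0.017, +0.011 or +0.006.

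**When would extrapolation trigger the fallback?** Assume 20% extrapolated counts as too much. A subject exceeds it above h = 72 × ln2/ln5 = 31.0 h if sampled to 72 h, and above 120 × ln2/ln5 = 51.7 h if sampled to 120 h. A majority of 48 active subjects is 25; the 72 h cohorts hold 4 × 6 = 24.
- At 20 h, extrapolation is 8.2% at 72 h and 1.6% at 120 h: no trigger.
- At a geometric mean of 31 h, with log-normal between-subject CV of 20-40% in half-life (assumed), about 12 to 14 of 48 exceed 20%, and the chance of 25 or more is below 0.1%.
- At 40 h and CV 20% (log SD 0.198), expected counts are 24 × 0.90 = 21.6 from the 72 h cohorts and 24 × 0.098 = 2.3 from the others, about 24 in all. So roughly 40 h is needed for a near-even chance.

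**If escalation stops early.** With a top dose of 260 mg, the 72 h cohorts hold 24 of 36 active subjects, a majority by themselves. The slope factor is 2.634/7.724 = 0.341 and the margin ln(1.25)/ln(26) = 0.068. At 20 h the bias is 0.341 × 0.0703 = +0.024 (35%); at 31 h it is 0.341 × 0.152 = +0.052 (76%). If all subjects shared one half-life, just above 31 h would suffice. With the spread above, 19 of 36 needs about 36 h, where f(72) = 75.0%, f(120) = 90.1%, and the bias is 0.341 × 0.183 = +0.062 (91%).

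**Effect on the decision.** Simulation with true beta = 1, six per dose, eight doses and 40,000 runs gives these chances of confirming proportionality (CVs are assumed):

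| Between-subject CV | No step | Step at 20 h | Step at 30 h |
|---|---|---|---|
| 15% | 93% | 66% | 13% |
| 20% | 67% | 44% | 10% |
| 30% | 12% | 9% | 4% |

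False rejection is at most about 3% in every case run. For CVs of 15-30%, the lack-of-fit pre-test flags the step in 6-7% of runs at 20 h and 8-16% at 30 h, against 5% by chance, so it is a weak safeguard.

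**The case against.** The strongest reply is that the fallback will seldom be used. The extension to 120 h covers five half-lives at 20 h, extrapolation at that half-life is small even at 72 h, and the majority condition cannot be met by the 72 h cohorts alone if all eight cohorts are run. A reader might take 31 h, the point where 20% is extrapolated at 72 h, as a typical trigger. With the full set of cohorts it is not; about 40 h is needed, twice what was observed. That part stands. It is weaker if escalation stops at 160, 260 or 380 mg, which section 1.4 foresees as possible, because the 72 h cohorts are then 24 of 30, 36 or 42. The other stated example, poor ke, can arise at any half-life. The 20 h figure applies to that route, where the bias may be small.

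It also stands that mono-exponential decline overstates the bias, that this is a secondary analysis in an exploratory trial, and that at a CV of 30% or more the test is uninformative anyway.

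It does not stand that the matter can be left to the announced PK analysis plan. The protocol itself fixes the fallback variable. The optional analysis on a restricted dose range escapes the step only if it stays within 10-80 mg or within 160-500 mg.

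A reader might also infer a mismatched renal clearance, since urine amounts are the "Total amount excreted over 24 h and 72 h" and no AUC0-72 is listed. The protocol gives no formula for CLr, and Ae(0-24) with AUC0-24 is a matched pair already planned. That inference is not supported.

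**Conclusion.** The fallback is wrong as written: the sampling schedule was split and the fallback variable was not adapted to it. The direction of the bias is certain whenever the fallback is used on doses from both sampling groups. Its size depends on half-life and on the shape of the decline: at most 41% of the margin at the observed 20 h, and above the whole margin at the roughly 40 h needed for extrapolation to trigger the rule with eight cohorts. The 20% threshold, the CVs, and half-lives other than 4, 11 and 20 h are assumptions.

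Two stronger readings are not supported. The planned tests on AUC0-∞ and Cmax are not biased by this. Nor would a proportional drug usually be declared non-proportional; the usual result is that the CI crosses the upper bound and no conclusion is drawn.

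Apart from the fallback, AUC0-t/D carries a false step between 80 and 160 mg of up to about 7% at 20 h (ratio 1.073). This is minor, since AUC0-∞/D, Cmax/D and AUC0-24 are tabulated beside it, but it should be labelled.

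**What to change.** In section 11.1.3, replace AUC0-t as the fallback with AUC0-72, for example: *if AUC0-∞ is unreliable in a majority of subjects, dose proportionality will be assessed on AUC0-72 in all cohorts*. Add AUC0-72 to the plasma parameters in sections 3.1.2 and 6.1.1. Footnote AUC0-t and AUC0-t/D in the summaries as not comparable between the 10-80 mg and 160-500 mg cohorts.

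The cost is one sentence, one derived parameter and a footnote. The 72 h sample is scheduled in every cohort, so no visit or blood draw is added.

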Physical examination, neurological examination, ECGs, vital signs and questionnaires: Physical examination, neurological examinations, ECGs, vital signs and questionnaires (C-SSRS, Bond and Lader VAS) recorded during the study will be individually listed and quantitative parameters will be summarised by using descriptive statistics. For vital signs and ECG parameters, all values recorded during the study will be individually listed and flagged for abnormalities and for clinical significance (assessed by investigator). In addition, values and abnormalities (not clinically significant and clinically significant) will be described by dose group and overall, at screening, study baseline (D-1, or D1 predose), each evaluation under treatment phase and at the end of the study. Change between the value at baseline and the value at each evaluation under treatment phase and at end of study visit will be described for each parameter by dose group and overall.

Laboratory parameters: All laboratory values recorded during the study will be individually listed and flagged for values outside reference ranges and for clinical significance (assessed by investigator). Quantitative parameters will be summarized by descriptive statistics. Values, position according to laboratory range and clinical significance assessment will be described at screening, D-1 (baseline) and at D2, D4 and D6 (only for the cohorts 160 mg, 260 mg, 380 mg and 500 mg) by dose group and overall. Change between the value at baseline and the value at post-dose visits will be described for each parameter by dose group and overall. All quantitative and qualitative urinary test results will be listed, sorted dose group, visit and subject.

Pharmacokinetic parameters:

Plasma concentrations will be summarized by dose level and time point. The derived PK parameters will be listed by subject and summarized by dose level.

In addition, the hypothesis that AUC and C_{max} are dose proportional will be formally tested using a power model approach.

Pharmacodynamic parameters:

ECG parameters will be summarized by dose level and time points on actual values and changes from baseline.

Placebo corrected changes from baseline ($\Delta\Delta$) will be calculated with their 90% CI for each dose level and time points and displayed.

Subjects meeting predefined criteria for ECG parameters abnormality and results of the morphological analysis will be summarized by dose level using count and percentage.

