7. ASSESSMENT OF PHARMACODYNAMIC EVALUATION

Subjects will be resting in a quiet supervised setting with minimal stimulation (e.g. no television, loud music, computer games, cell phones, handled music player, etc.) and lay in a supine position for 15 min $_{\text{Temp-UPC-853-C}}$ du 07/08/2017

before each nominal PK time point for the duration of the ECG sampling period. The ECG extraction window will precede any PK blood draw (within 10 minutes prior to PK sampling). All other exams should be done after the ECG extraction period.

Holter recordings will be archived. Analyses will be conducted at the end of the trial by Banook Groupe, Nancy, France if decision to progress to Multiple Ascending Dose (MAD) study is taken or after MAD in order to pool data from SAD and MAD studies. Subjects will be in resting position from -70 to -15 minutes prior to dosing in order to insure proper quality of the recording for ECG extraction pre-dose at T-60 min, T-40min and T-20min. Windows of ECG extractions for each timepoint are defined in the Banook Groupe Scope of Work document.

The Holter data collected in this trial will not be part of the trial's clinical data base.

In case the Holter extracted data are analysed, the following analyses are planned and will be reported in a separate report:

For each selected post-dose PK time-point, Triplicate ECG with at least a 1 min interval will be extracted from the Holter recording at the cardiac core laboratory at the following time points:

On D1 and on D1 to D2: T0 (pre-dose 3 times triplicate ECG as described above), T0h30min, T1h, T1h30 (only for the cohorts 10 mg, 20 mg, 40 mg, 80 mg), T2h, T2h30, T3h, T4h, T5h (only for the cohorts 160 mg, 260 mg, 380 mg and 500 mg), T6h, T9h, T12h, T24h. T0h corresponds to the administration time reference at which subjects will receive the study drug throughout the study (around 8:00 am).

The Holter-extracted triplicate parameters (RR, HR, PR, QRS, and QT) would be averaged to obtain one single value per time point. On Day 1, three pre-dose triplicates will be extracted and averaged to establish the baseline value.

Changes from baseline with the recorded Holter (Day 1) will be calculated for each parameter:

- Categorical analysis for QT, QTcF, QTcB, ΔQTcF and ΔQTcB according to the thresholds defined below.
- ECG morphological analysis.

The pre-defined thresholds for the categorical analysis for maximum actual values will be:

- QTc interval > 450 ms
- QTc interval > 480 ms

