- QT/QTc interval > 500 ms

and for maximum changes from baseline:

- ΔQTc interval > 30 ms
- ΔQTc interval > 60 ms

All parameters and their changes from baseline will be summarized by dose regimen and time-point (including Δ HR, Δ RR, Δ PR, Δ QRS, Δ QT). Placebo group extracts will be used for the double-delta analysis of QT.

QT interval calculation would be manually checked by a cardiologist.

A concentration-response analysis between $\Delta QTcF$ and DNDI-6148 concentrations will be performed on ECG data issued from Holter extraction. $\Delta\Delta QTcF$ with their 90% CI will be estimated from the model at each dose Cmax geometric means.

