Categorical analysis consisting in counts and percentages of abnormal values per dose level will be performed for HR, QTc, PR and QRS according to regulatory thresholds for raw data and changes from baseline.

Treatment emergent morphological findings will be summarized as counts and percentage of subjects presenting at least one finding by dose level.

Concentration-response relationship will be investigated between change from baseline in QTcF and DNDI-6148 concentrations. First, graphics of change from baseline in QTcF and concentrations of DNDI-6148 will be generated in order to visualize the overall pattern of each relationship. Modelling of each of these graphics will then be performed by means of linear or nonlinear mixed model.

For each compound, a model will be selected according to the overall precision of the model towards observed data and diagnostic plots. Using these models, predictions of changes from baseline at concentrations of interest (e.g. Cmax) will be obtained from the concentration-response models with their 90%CI.

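### Section 11.1.3 counts abnormal values in the Holter categorical ECG analysis, whereas the Synopsis counts subjects and Section 7 uses maxima; the percentages can differ by a factor of 1 to 11

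*Protocol*

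**What the plan says.** Three places in the Protocol describe the categorical part of the same Holter ECG analysis.

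- **Synopsis, Statistics, Pharmacodynamic parameters:** "Subjects meeting predefined criteria for ECG parameters abnormality and results of the morphological analysis will be summarized by dose level using count and percentage". The unit is the subject.
- **Section 7:** "The pre-defined thresholds for the categorical analysis for maximum actual values will be" QTc above 450 ms, QTc above 480 ms and QT/QTc above 500 ms, "and for maximum changes from baseline" a QTc change above 30 ms and above 60 ms. A maximum implies one result per subject, although the word subjects is not used. The parameters named are QT, QTcF, QTcB and the changes in QTcF and QTcB.
- **Section 11.1.3, Pharmacodynamic:** "Categorical analysis consisting in counts and percentages of abnormal values per dose level will be performed for HR, QTc, PR and QRS", against regulatory thresholds that are not listed. The unit is the value. The next sentence, on morphology, uses the other unit: "counts and percentage of subjects presenting at least one finding by dose level".

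Section 11.1.3 also says that triplicates are averaged to a single value at each time point. Nothing states that both tabulations are intended, or which section governs.

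**The concern.** A categorical outlier table is meant to show how many subjects crossed a threshold. If values are counted instead, repeated measurements on one subject enter as though they were separate observations. A short-lived exceedance near Cmax is then diluted by that subject's other time points, and one persistently high subject can dominate a dose level. Because the sections differ, the analyst could follow either and still claim to follow the protocol, possibly after seeing the data.

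The parameter lists differ as well. QT appears only in Section 7; HR, PR and QRS appear only in Section 11.1.3, with no stated thresholds.

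**Working it through.** The protocol gives no figure for this table, so there is none to reproduce. The size follows from its own schedule.

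**Inputs**
- Post-dose extractions (Section 7): "T0h30min, T1h, T1h30 (only for the cohorts 10 mg, 20 mg, 40 mg, 80 mg), T2h, T2h30, T3h, T4h, T5h" (the last only for 160 to 500 mg), then "T6h, T9h, T12h, T24h".
  - 10 to 80 mg: 0.5, 1, 1.5, 2, 2.5, 3, 4, 6, 9, 12, 24 h = 11.
  - 160 to 500 mg: 0.5, 1, 2, 2.5, 3, 4, 5, 6, 9, 12, 24 h = 11.
- One averaged value per time point (Section 11.1.3).
- 6 active and 2 placebo subjects per cohort (Section 11.2); 8 cohorts, so 2 × 8 = 16 placebo subjects if pooled.

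**Formula**
Let s be the number of subjects with at least one abnormal value and v the number of abnormal values, with s ≤ v ≤ 11s.
- Percentage of subjects = s/6.
- Percentage of values = v/(6 × 11) = v/66.
- Ratio = (s/6)/(v/66) = 11s/v.

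The ratio is 11 when each affected subject has exactly one abnormal value (v = s), and 1 when every value of each affected subject is abnormal (v = 11s). Pooled placebo (16 × 11 = 176 values) has the same bounds.

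**Examples per dose level**

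| Pattern | Subjects | Values | Ratio |
|---|---|---|---|
| 1 subject, 1 value | 1/6 = 16.7% | 1/66 = 1.5% | 11.0 |
| 3 subjects, 1 value each | 3/6 = 50.0% | 3/66 = 4.5% | 11.0 |
| 1 subject, 6 values | 1/6 = 16.7% | 6/66 = 9.1% | 1.8 |
| 1 subject, 11 values | 1/6 = 16.7% | 11/66 = 16.7% | 1.0 |

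**Ranking of doses (hypothetical counts)**
- Dose A, 1 subject above at 8 times: 16.7% of subjects, 8/66 = 12.1% of values.
- Dose B, 4 subjects above once each: 4/6 = 66.7% of subjects, 4/66 = 6.1% of values.

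B ranks higher by subjects, A by values. The smallest such reversal is 2 subjects with 2 values in total against 1 subject with 3 values.

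**Typical size, under an assumption that is not in the documents**
Suppose a subject's 11 values are equicorrelated normal with correlation ρ, and each is abnormal with probability p. With t the upper p quantile, X the standard normal subject effect and Φ the normal distribution function, the expected subject percentage is 1 − E[Φ((t − √ρ·X)/√(1 − ρ))^11]. Divided by p:

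| ρ | p = 1% | p = 2% | p = 5% |
|---|---|---|---|
| 0 | 10.47 | 9.96 | 8.62 |
| 0.5 | 7.13 | 6.35 | 5.18 |
| 0.9 | 2.95 | 2.70 | 2.36 |

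Exceedances that cluster within subjects bring the gap well below 11.

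**The case against.** The strongest counter-argument is that Section 11.1.3 states no denominator and does not say that time points are pooled. Read together with Section 7, its abnormal values could be abnormal maxima, one per subject, and would then agree with the Synopsis. It is true that the 66-value denominator is inferred. It is also true that only the Synopsis names subjects and only Section 7 names the maximum. But the reading is strained: Section 11.1.3 itself defines one value per time point and changes to subjects in its next sentence, so values most naturally means time-point values.

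Table units are often settled in a statistical analysis plan, and Section 11.1.3 announces one, under its pharmacokinetic heading. That would excuse silence. It does not excuse two different units in the protocol itself.

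The parameter lists may be complementary, with Section 11.1.3 adding HR, PR and QRS. That is possible, but those three then have no threshold anywhere in the protocol.

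A reader might also infer that the dose-level cardiac conclusion depends on which section is followed, or that a brief prolongation could be hidden. The documents do not support this. The same analysis plans individual listings, summaries by dose and time point, and a concentration-QTcF model with 90% confidence intervals; the Synopsis adds placebo-corrected changes. Holter data are analysed only if the programme proceeds to the multiple-dose study, or after it. They stay outside the clinical database and go to a separate report. Escalation uses central reading of the 12-lead ECGs (Sections 3.3.3.2 and 8.1.1.3), and the stopping rules in Section 3.5 contain no Holter criterion.

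**Conclusion.** The inconsistency in the counting unit is real, and following Section 11.1.3 literally gives a different table from the one in the Synopsis. The percentages differ by a factor of 1 to at most 11. The upper bound assumes post-dose values only, complete data in 6 active subjects, and one exceedance per affected subject. A reversed ranking of doses is arithmetically possible but rests on invented counts; nothing in the documents shows that it will occur. The consequence is limited to one exploratory, conditional table. It is worth correcting because the correction costs almost nothing and keeps the unit from being chosen after the results are known.

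**What to change.** Amend the pharmacodynamic part of Section 11.1.3 before any Holter data are analysed:

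1. Report, by dose level, the number and percentage of subjects with at least one post-dose value, or change from baseline, meeting the criterion. The denominator is subjects with post-dose data.
2. For QT/QTc, compare each subject's maximum with the thresholds listed in Section 7.
3. Reconcile the parameter lists of Sections 7 and 11.1.3. For HR, PR and QRS, either predefine thresholds and their direction (high or low) or remove them from the categorical analysis. The Section 7 list does not cover them, and a rule based only on the maximum would miss a low HR.
4. Label any count of individual values as supplementary.

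The cost is a wording change with no new data. The one drawback is coarser percentages, in steps of 1/6 per dose level.
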